2 LIST OF ABBREVIATIONS AND DEFINITION OF TERMS

| AM | morning |
|------------------|---|
| BID | twice daily |
| CDC | Centers for Disease Control and Prevention |
| C _{max} | maximum concentration |
| COVID-19 | coronavirus disease 2019 |
| DDC | direct data capture |
| DMC | data monitoring committee |
| GCP | Good Clinical Practice |
| ICF | informed consent form |
| ICH | International Council for Harmonization |
| IEC | Independent Ethics Committee |
| IP | investigational product |
| IRB | Institutional Review Board |
| ITT | intent-to-treat |
| MDI | metered-dose inhaler |
| MedDRA | Medical Dictionary for Regulatory Activities |
| PM | evening |
| SAP | statistical analysis plan |
| SARS-CoV-2 | Severe Acute Respiratory Syndrome Coronavirus 2 |
| WHO | World Health Organization |

3 INTRODUCTION

3.1 Background Information on Coronavirus Disease 2019 (COVID-19)

There is currently an outbreak of respiratory disease caused by a novel coronavirus that was first detected in Wuhan City, Hubei Province, China, and that has now been detected in many locations internationally, including cases in the United States. The virus has been named Severe Acute Respiratory Syndrome Coronavirus 2 (SARS-CoV-2) and the disease it causes has been named Coronavirus Disease 2019 (COVID-19). On January 31, 2020, the Department of Health and Human Services issued a declaration of a public health emergency related to COVID-19 and on March 13, 2020, the President declared a national emergency in response to COVID-19.

The United States Centers for Disease Control and Prevention (CDC) has stated that symptoms compatible with COVID-19 include subjective or measured fever, cough, or difficulty breathing, and may present within 2 to 14 days after exposure. Reported illnesses have ranged from mild symptoms to severe illness and death for confirmed COVID-19 cases.

Currently there are no approved treatments for COVID-19. Innovators are looking at products in a variety of areas, including the assessment of antiviral drugs that might treat the specific virus, as well as host targets, such as interleukin-6 receptor inhibitors that may be helpful in reducing lung inflammation and improving lung function in COVID-19 patients, thereby potentially slowing the progression of severe respiratory symptoms.

3.2 Background Information on Ciclesonide and Rationale for Use in COVID-19

Alvesco[®] (ciclesonide) Inhalation Aerosol is an inhaled corticosteroid that has been approved in the United States for the indication of maintenance treatment of asthma as prophylactic therapy in adult and adolescent patients 12 years of age and older (Alvesco[®] Inhalation Aerosol US prescribing information, 2019). Alvesco (ciclesonide) Inhalation Aerosol is administered by oral inhalation employing a pressurized metered-dose inhaler (MDI) and is available in 2 strengths (80 μ g/actuation and 160 μ g/actuation). Additional summary information regarding Alvesco (ciclesonide) Inhalation Aerosol is provided in the product labeling (Alvesco[®] Inhalation Aerosol US prescribing information, 2019).

Systemic glucocorticoid therapy is not currently indicated in patients with pneumonia or COVID-19 because of the potential for prolonging viral replication, as observed in patients with Middle East Respiratory Syndrome Coronavirus (CDC, 2020). However, inhaled glucocorticoids, such as ciclesonide, may demonstrate clinical benefit in patients with less severe symptoms of COVID-19 (Fu et al, 2020; Zhai et al, 2020).

Institut Pasteur Korea has recently identified ciclesonide as a potential candidate against COVID-19 infection based on a screening of approximately 3000 drugs. A total of 48 drugs were initially pre-selected based on an assay of SARS-CoV and were further tested for antiviral activity against SARS-CoV-2. Of these, 24 drugs (including ciclesonide) showed antiviral activity against SARS-CoV-2 (Jeon et al, 2020). This finding was corroborated in a recent publication by Matsuyama et al, 2020, in which it was reported that ciclesonide blocked SARS-CoV-2 replication in cultured cells at low concentrations. Furthermore, a small number

(n = 3) of patients in Japan with confirmed COVID-19 infection, all over 65 years of age and receiving supplemental oxygen, were treated with ciclesonide and demonstrated clinical improvement in 2 days (Puiu, 2020), providing additional support for continued study of ciclesonide in the treatment of COVID-19. Interestingly, an underlying mechanism for the suppression of viral infection by ciclesonide has been revealed by the isolation of a drug-resistant mutant. Isolation of this mutant indicated that NSP15, a viral riboendonuclease, is a molecular target of ciclesonide (Matsuyama et al, 2020). Thus, it is reasonable to consider that ciclesonide may exhibit a direct-acting antiviral activity in addition to its intrinsic anti-inflammatory function and, therefore, has the potential to manifest dual roles (antiviral and anti-inflammatory) in the treatment of COVID-19 infection.

The systemic bioavailability is low for inhaled glucocorticoids (mean maximum concentration $[C_{max}]$ of des-ciclesonide [pharmacologically active metabolite of ciclesonide prodrug] in plasma following once daily 320 µg inhaled ciclesonide was 0.369 ng/mL), whereas oral glucocorticoids such as prednisone and prednisolone have a mean C_{max} of 2.4 and 18.1 µg/L/1 mg dose, respectively (Czock et al, 2005). Therefore, it is hypothesized that use of Alvesco (ciclesonide) Inhalation Aerosol will reduce inflammation and viral replication in the lung in patients with COVID-19 while limiting the risk of systemic toxicities. These effects have the potential to decrease symptom burden and shorten disease duration.

From data available to date, it appears that patients with comorbidities of hypertension and diabetes mellitus are at most risk when exposed to COVID-19 (Yang et al, 2020; Zhang et al, 2020). There is currently limited data describing how COVID-19 affects people with asthma. In a study of 140 cases of COVID-19 patients no link to asthma was observed (Zhang et al, 2020). The data reported thus far may support the hypothesis that inhaled corticosteroids could provide a protective effect for these patients against COVID-19.

Covis Pharma B.V. (Covis) is assessing the safety and efficacy of Alvesco (ciclesonide) Inhalation Aerosol in non-hospitalized patients with symptomatic COVID-19 infection in this multicenter, randomized, double-blind, placebo-controlled study.

3.3 Rationale for Dose Selection and Treatment Duration

The dose of ciclesonide selected for use in this study is 320 μ g twice daily (BID), which is the currently approved highest recommended starting dose for Alvesco Inhalation Aerosol (Alvesco[®] Inhalation Aerosol US prescribing information, 2019). Patients will be instructed to self-administer Alvesco Inhalation Aerosol (hereafter referred to as ciclesonide MDI) or placebo MDI at a frequency of BID concurrently with standard supportive care for 30 days. The duration of treatment is consistent with the limited information available regarding time to discharge for patients in China without hypoxemia or respiratory distress (mean time to discharge 17 ± 4 days) (Pan et al, 2020).

Because there are no proven or approved treatments for COVID-19, all patients will also receive standard supportive care according to the treating facility's standard.

3.4 Rationale for Subject Population

Patients with confirmed COVID-19 infection who are not hospitalized and presenting with mild to moderate disease represent the largest population (80%; Verity et al, 2020) and have been determined as the population with the highest likelihood of benefit from ciclesonide treatment due to earlier intervention potentially decreasing viral replication and, therefore, viral load. It is hypothesized that treatment with ciclesonide will decrease duration of clinical symptoms, thereby decreasing the severity of disease.

The study will enroll male and female patients 12 years of age or older, the population for which Alvesco has been determined to be safe. Furthermore, patients who have been treated with inhaled or intranasal corticosteroids within 14 days of screening/enrollment/randomization or any patient who has received oral corticosteroids within 90 days of screening/enrollment/ randomization will be excluded from the study in order to minimize potential confounding of data from background steroid use.

4 STUDY OBJECTIVES

4.1 **Primary Objective**

The primary study objective is to assess whether treatment with ciclesonide MDI plus standard supportive care results in improved time to alleviation of COVID-19-related symptoms of cough, dyspnea, chills, feeling feverish, repeated shaking with chills, muscle pain, headache, sore throat, and new loss of taste or smell compared with placebo plus standard supportive care in non-hospitalized patients with symptomatic COVID-19 infection.

4.2 Secondary Objectives

The secondary study objectives are:

- to assess whether treatment with ciclesonide MDI plus standard supportive care reduces the incidence of hospital admissions or death compared with placebo plus standard supportive care in non-hospitalized patients with symptomatic COVID-19 infection
- to assess whether treatment with ciclesonide MDI plus standard supportive care reduces all-cause mortality compared with placebo plus standard supportive care in non-hospitalized patients with symptomatic COVID-19 infection
- to assess whether treatment with ciclesonide MDI plus standard supportive care reduces COVID-19-related mortality compared with placebo plus standard supportive care in non-hospitalized patients with symptomatic COVID-19 infection
- to assess whether treatment with ciclesonide MDI plus standard supportive care reduces the incidence of subsequent emergency department visits or hospital admissions for reasons attributable to COVID-19 compared with placebo plus standard supportive care in non-hospitalized patients with symptomatic COVID-19 infection
- to assess whether treatment with ciclesonide MDI plus standard supportive care increases the percentage of patients with alleviation of COVID 19-related symptoms of cough, dyspnea, chills, feeling feverish, repeated shaking with chills, muscle pain, headache, sore throat, and new loss of taste or smell compared with placebo plus standard supportive care in non-hospitalized patients with symptomatic COVID-19 infection
- to assess whether treatment with ciclesonide MDI plus standard supportive care increases the time to hospital admission or death compared with placebo plus standard supportive care in non-hospitalized patients with symptomatic COVID-19 infection
- to assess the impact of treatment with ciclesonide MDI plus standard supportive care on oxygen saturation levels compared with placebo plus standard supportive care in non-hospitalized patients with symptomatic COVID-19 infection
- to assess the impact of treatment with ciclesonide MDI plus standard supportive care on COVID-19 viral load compared with placebo plus standard supportive care in non-hospitalized patients with symptomatic COVID-19 infection

• to assess the safety of ciclesonide MDI plus standard supportive care compared with placebo plus standard supportive care in non-hospitalized patients with symptomatic COVID-19 infection

4.3 Estimands

The International Council for Harmonization (ICH) *Guidance: Addendum on Estimands and* Sensitivity Analysis in Clinical Trials to the Guideline on Statistical Principles for Clinical Trials E9(R1) was adopted on 20 November 2019. This section will describe the planned analyses for this protocol in the context of this guideline.

An estimand is a description of the treatment effect to address the clinical/scientific question of interest posed by the trial objective.

4.3.1 Primary Endpoint Estimand

The attributes of the estimand for the primary endpoint of this trial are:

- 1. Treatment regimens: ciclesonide and placebo
- 2. Populations of interest: patients meeting inclusion/exclusion criteria grouped according to randomized treatment assignment reflect the target population
- Patient-level outcome: time to alleviation of COVID-19-related symptoms of cough, dyspnea, chills, feeling feverish, repeated shaking with chills, muscle pain, headache, sore throat, and new loss of taste or smell, defined as symptom-free for a continuous period of ≥ 24 hours (ie, ≥ 3 AM/PM assessments) by day 30
- 4. Intercurrent events: regardless of the use of rescue medications, protocol violations, or investigational product discontinuation
- 5. Population-level summary measure: difference in survival distributions between treatment regimens

The **treatment-policy strategy** for this estimand is the difference in survival distributions of time to alleviation of COVID-19-related symptoms of cough, dyspnea, chills, feeling feverish, repeated shaking with chills, muscle pain, headache, sore throat, and new loss of taste or smell, defined as symptom-free for a continuous period of ≥ 24 hours (ie, ≥ 3 AM/PM assessments) by day 30 between those assigned to ciclesonide and those assigned to placebo, regardless of patient's use of rescue medications, protocol violations, or investigational product discontinuation. Therefore, for all patients in the intent-to-treat (ITT) analysis set, all observed on-study data will be analyzed in accordance with the definition set forth above for intercurrent events.

Since death and hospitalization are not part of the primary endpoint patient level-outcome definition, a composite strategy will be used to handle these situations. If a patient dies or is hospitalized, regardless of when it occurs, the value attributed in that scenario would be a failure to respond or achieve alleviation of COVID-19-related symptoms by the end of the study (day 30). This ascribes a sufficiently unfavorable outcome under these scenarios.

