4.3.2 Key Secondary Endpoint Estimand

The attributes of the estimand for the key secondary endpoint included in the multiplicity control procedure of this trial are:

- 1. Treatment regimens: ciclesonide and placebo
- 2. Populations of interest: patients meeting inclusion/exclusion criteria grouped according to randomized treatment assignment reflect the target population
- 3. Patient-level outcome: binary indicator of alleviation of COVID-19-related symptoms of cough, dyspnea, chills, feeling feverish, repeated shaking with chills, muscle pain, headache, sore throat, and new loss of taste or smell, defined as symptom-free for a continuous period of \geq 24 hours (ie, \geq 3 AM/PM assessments) by day 14
- 4. Intercurrent events: regardless of the use of rescue medications, protocol violations, or investigational product discontinuation
- 5. Population-level summary measure: difference in response probabilities between treatment regimens

The **treatment-policy strategy** for this estimand is the difference in probabilities of alleviation of COVID-19-related symptoms of cough, dyspnea, chills, feeling feverish, repeated shaking with chills, muscle pain, headache, sore throat, and new loss of taste or smell, defined as symptom-free for a continuous period of ≥ 24 hours (ie, ≥ 3 AM/PM assessments) by day 14 between those assigned to ciclesonide and those assigned to placebo, regardless of patient's use of rescue medications, protocol violations, or investigational product discontinuation. Therefore, for all patients in the ITT analysis set, all observed on-study data will be analyzed in accordance with the definition set forth above for intercurrent events.

Since death and hospitalization are not part of this key secondary endpoint patient level-outcome definition, a composite strategy will be used to handle these situations. If a patient dies or is hospitalized, then the value attributed in that scenario would be failure to achieve alleviation of COVID-19-related symptoms which ascribes the most unfavorable value.

Estimands for other secondary efficacy endpoints included in the multiplicity control procedure (section 10.7.3) will be described in the Statistical Analysis Plan (SAP).

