Following signature of the informed consent form (ICF), patients meeting inclusion/exclusion criteria will be randomly assigned (1:1) to treatment with ciclesonide MDI 320 µg BID (AM and PM) plus standard supportive care (hereafter referred to as the ciclesonide arm) or placebo MDI BID (AM and PM) plus standard supportive care (hereafter referred to as the placebo arm). During the initial screening/enrollment/randomization visit, patients will be instructed on how to self-administer a MDI and will be discharged home with a 30-day supply of investigational product (ie, either ciclesonide MDI or placebo MDI), standard supportive care, a pulse oximeter for at-home oxygen saturation level monitoring, and an electronic diary (eDiary). A nasopharyngeal sample for viral load analysis will also be obtained at the initial screening/enrollment/randomization visit. Patients will be instructed to record self-administration of investigational product and oxygen saturation levels in the eDiary. Prior to self-administration of the investigational product (ie, within 1 hour of administration), patients will also complete and record assessments in the eDiary of severity of COVID-19-related symptoms of cough, dyspnea, chills, and feeling feverish (based on a 4-point scale where 0 = absent, 1 = mild, 2 = moderate, and 3 = severe) and the presence/absence of COVID-19-related symptoms of repeated shaking with chills, muscle pain, headache, sore throat, and new loss of taste or smell. Qualified healthcare providers will contact patients on days 2, 4, 6, 8, 10, 12, 14, 21 ± 2 days, and 30 ± 2 days for a health status check, to collect adverse event and concomitant medication information, and to confirm/clarify information recorded in the eDiary. During these patient contacts, medical advice commensurate with standard of care for reported symptoms or adverse events will be provided. On day 30 (window of + 2 days), the patient will return to the study site for collection of a nasopharyngeal sample for viral load analysis and to return the eDiary and investigational product (ie, used and unused MDIs). Qualified healthcare providers will contact patients on day 37 ± 4 days and day 60 ± 7 days to collect follow-up safety and outcome data (the follow-up period).

Patients (or their representatives) will be asked to notify study personnel directly in the event they visit an emergency department or are hospitalized during their participation in the study.

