Patient duration on study is expected to be approximately 60 days, including the screening/ enrollment/randomization visit, the 30-day treatment period and the subsequent follow-up period. In the event the patient requires hospitalization during the 30-day treatment period, the patient will discontinue investigational product and scheduled follow-up procedures but will continue to be followed for the outcome of hospitalization and ongoing adverse events (see section 5.3.4).

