7 STUDY ASSESSMENTS AND PROCEDURES

7.1 Efficacy

7.1.1 Efficacy Endpoints

The primary efficacy endpoint is:

• Time to alleviation of COVID-19-related symptoms of cough, dyspnea, chills, feeling feverish, repeated shaking with chills, muscle pain, headache, sore throat, and new loss of taste or smell, defined as symptom-free for a continuous period of ≥ 24 hours (ie, ≥ 3 AM/PM assessments) by day 30

The secondary efficacy endpoints for the study are:

- Percentage of patients with hospital admission or death by day 30
- All-cause mortality by day 30
- COVID-19-related mortality by day 30
- Percentage of patients with subsequent emergency department visit or hospital admission for reasons attributable to COVID-19 by day 30
- Percentage of patients with alleviation of COVID-19-related symptoms of cough, dyspnea, chills, feeling feverish, repeated shaking with chills, muscle pain, headache, sore throat, and new loss of taste or smell, defined as symptom-free for a continuous period of ≥ 24 hours (ie, ≥ 3 AM/PM assessments) by day 7, by day 14, and by day 30
- Time to hospital admission or death
- Change from baseline in oxygen saturation levels
- Change from baseline in COVID-19 viral load in nasopharyngeal sample at day 30

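### The death-or-hospitalisation failure rule has no time limit, so an admission after day 30 (or after day 14 for the key secondary) can reverse an outcome already decided

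*Combined protocol and SAP*

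**What the plan says.** The primary outcome in Section 4.3.1 is time to alleviation by day 30, with alleviation "defined as symptom-free for a continuous period of" at least 24 hours, that is, three or more consecutive diary assessments. It can therefore be met early in the treatment period.

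For death and hospitalisation the section adopts a composite strategy: "If a patient dies or is hospitalized, regardless of when it occurs, the value attributed in that scenario would be a failure to respond" or to achieve "alleviation of COVID-19-related symptoms by the end of the study (day 30"). It gives no last qualifying date, no restriction on cause and no exception for a patient who has already met the definition.

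Section 4.3.2 does the same for the day-14 responder endpoint: "If a patient dies or is hospitalized, then the value attributed in that scenario would be failure to achieve alleviation of COVID-19-related symptoms". The clause about timing is absent here, but no event window is given either. Section 7.1.1 also lists responder endpoints "by day 7, by day 14, and by day 30"; estimands for the other secondary endpoints in the testing sequence are left to the SAP.

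On follow-up, Section 5.1 says "Patient duration on study is expected to be approximately 60 days" and that healthcare providers will "contact patients on day 37 ± 4 days and day 60 ± 7 days to collect follow-up safety and outcome data". Patients are asked to report any hospitalisation throughout their participation. Sections 10.7.1 to 10.7.3 neither repeat nor limit the rule.

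**The concern.** An endpoint defined by day 30 or by day 14 should be settled by what happens up to that day. Under the literal rule it is not. A patient symptom-free on day 6 and admitted on day 45 for an unrelated reason is coded as not alleviated by day 30. A day-14 responder admitted on day 20 can lose the response.

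Symptom recording ends with day 30 (Section 5.3.2), so a patient first admitted later should have a diary running to the endpoint's own day. Recoding that patient fills no gap in the data; it replaces an observed outcome.

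Two things are at stake. The first is reproducibility: the unlimited timing clause and the description of day 30 as the end of the study, beside a 60-day study duration, support two different codings of the primary endpoint. The second is meaning: late admissions of any cause can move a result that will be reported as symptom alleviation.

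**Working it through.** **Plan's own figures.** Section 10.1 gives medians of 7 and 11 days, a hazard ratio of about 1.58, α = 0.05, 90% power, 201 events and 232 patients, raised to 400. Schoenfeld, two-sided: 4 × (1.960 + 1.282)² / (ln 1.58)² = 42.03 / 0.2092 ≈ 201 events, an exact match. With exponential times, the chance of alleviation by day 30 is 1 − 2^(−30/7) = 0.949 and 1 − 2^(−30/11) = 0.849, mean 0.899. Freedman's formula gives 208 events, and 208 / 0.899 gives 232 patients. These figures stand; the point does not alter them.

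**Assumptions for the size.** The documents give no admission or death rate. I take a share q of each arm with an event, uniform over days 0 to 60 and independent of recovery; 200 patients per arm; no dropout. A failure is carried as unrecovered to day 30.

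**Recoveries erased at q = 5%** (10 patients with an event per arm). Let P be the chance of alleviation by day 30 and m the mean of T × 1(T ≤ 30), which is 8.04 days on ciclesonide and 8.94 on placebo.

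- Any-time rule, per patient with an event: P − m/60 = 0.949 − 0.134 = 0.815 and 0.849 − 0.149 = 0.700. Total: 10 × 0.815 + 10 × 0.700 ≈ 15.1.
- Rule stopping at day 30: (30P − m)/60 = 0.340 and 0.275. Total: 3.4 + 2.8 ≈ 6.2.
- The difference, about 9 of roughly 357 recoveries, comes wholly from events after day 30.

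Simulation gave the same 15.1 and 6.2.

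**Power at 400 patients** (simulated, unadjusted log-rank test, 2,000 runs each, Monte Carlo standard error below 0.01):

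| Events per arm | Any time | To day 30 | Only before alleviation |
|---|---|---|---|
| 2% | 0.98 | 0.99 | 0.99 |
| 5% | 0.95 | 0.98 | 0.99 |
| 10% | 0.87 | 0.96 | 0.99 |

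**Unequal rates.** With 5% on ciclesonide and 2% on placebo, power is 0.87 under the any-time rule and 0.96 with the day-30 limit. With identical alleviation times (median 11 in both arms) but events in 5% on ciclesonide and 10% on placebo, the test rejects in about 15% of trials under the any-time rule, 7.5% with the day-30 limit and 6% if only events before alleviation count (4,000 runs each).

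**Day-14 responder at q = 5%.** Without the rule, response is 1 − 2^(−14/7) = 0.750 and 1 − 2^(−14/11) = 0.586. Any-time rule: × 0.95 = 0.713 and 0.557, difference 0.156. Bounded at day 14: × (1 − 0.05 × 14/60) = × 0.988 = 0.741 and 0.579, difference 0.162.

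**The case against.** The strongest defence is that the authors mean day 30 as the horizon. Section 4.3.1 calls it the end of the study and Section 10.1 speaks of a 30-day study duration. On that view the timing clause means before or after alleviation, within 30 days. This reading is possible, and it is why the post-day-30 part is an ambiguity rather than a declared choice. It does not remove the ambiguity: in the sentence, day 30 dates the alleviation and not the admission, and Section 5.1 sets the study at about 60 days.

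Section 4.3.2 does not carry the timing clause, so reversal of a day-14 response is inferred from a missing window. That stands too.

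Counting an admission inside the window as failure, even after a symptom-free day, is a legitimate composite. Alleviation needs only 24 hours, and the plan gives its reason: such outcomes should receive an unfavourable value.

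A reader might infer that the Cox or Kaplan-Meier analysis is invalid because status depends on later events. The documents do not support that. The rule defines one outcome per randomised patient, known at database lock and compared by randomised arm. The excess rejections shown above reflect a real difference in the composite, not type I error for it.

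A reader might also infer that late admissions are counted twice in steps 7 to 9 of the testing sequence. Steps 7, 9, 10 and 11 stop at day 30, and step 7 requires a COVID-19 reason, so an unrelated day-45 admission enters none of them. Only step 8 states no horizon, and overlap between endpoints in a fixed sequence is not in itself a defect.

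**Conclusion.** The rule needs an event window. As written, it lets events after the endpoint's own day decide outcomes defined by day 30 or day 14, and it leaves the coding of the primary endpoint open.

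The size is modest at the planned 400 patients: at an assumed 5% per arm, about 9 extra recoveries are lost beyond the day-30 rule and power is about 0.95 instead of 0.98. It is negligible at 2% and larger at 10%. At 232 patients the loss at 5% would look bigger (0.79 against 0.85), but that is not the planned sample size. Dropout, which the plan does not quantify, would put the real trial somewhere between.

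The direction is not fixed. Equal rates, or more events on ciclesonide, weaken the result; more events on placebo can favour ciclesonide without any difference in alleviation. All of this rests on assumed rates, uniform timing and independence from recovery. The need for a window rests on the wording alone.

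**What to change.** - Section 4.3.1: replace the timing clause (the words between the two commas in the quoted sentence) with 'on or before day 30', and reconcile the description of day 30 as the end of the study with the 60-day duration.
- Section 4.3.2: add 'on or before day 14' to the death-or-hospitalisation sentence.
- SAP: use day 7 and day 30 for the corresponding responder endpoints.
- State explicitly whether an event after documented alleviation but inside the window reverses it. The plan's choice of failure may remain primary; add a sensitivity analysis in which only events before alleviation count as failure.

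The cost is wording plus one extra analysis on data already collected. No visit, sample size or test changes. Section 10 allows changes in statistical methods before unblinding to be documented in the SAP without an amendment. Admissions and deaths after day 30 would then not affect the symptom endpoints. They would still be captured as serious adverse events, and in the time to hospital admission or death if its horizon, which is not stated, runs past day 30.
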